Connecticut law requires reporting of the abuse of persons above the age of 60. During the consent process, participants will be notified of this legal requirement but reassured that investigators will make every effort to make the process confidential and comfortable for the participant, including a) keeping the participant's reporting confidential and b) involving the care team (clinician, nurses, and attendings), who can address patient's concerns around reporting, immediate safety concerns, and any concerns for retaliation or abandonment.

At the end of the consent process, the RA will review the subject's understanding of the study by asking the following question:

- What are you being asked to do?
- What questions is this study trying to answer?
- What are the potential risks and benefits of participating in this study?
- Can you withdraw from the study, and what should you do if you decide to withdraw?
- Do you understand that participation in this study is voluntary and is not part of your medical treatment?

10. **Risks:** Describe the reasonably foreseeable risks, including risks to subject privacy, discomforts, or inconveniences associate with subjects participating in the research.

There are no medical interventions in this study, the direct medical risks are minimal. However, identification of potential EM without adequate safeguards could increase the risk of physical harm, emotional harm, risk of neglect, and financial loss to the victim. In addition, EM Identification can potentially lead to adverse events

including:

- retaliation of a family member,
- an older adult may lose the caregiver or be abandoned by a caregiver, a family member or paid caregiver may be arrested / incarcerated.
- discharge of a patient to a long-term care or skilled nursing facility, which they may not be able to afford and the setting of which could be problematic for them,
- distress/anxiety during and/or after using the VOICES tool is a potential risk given the complex emotions typically associated with this phenomenon,
- participant may suffer from distress and/or anxiety when reviewing information and answer questions about EM during the study session,
- participant may suffer from distress and/or anxiety when he or she realizes that he she is a victim of EM based on the information received from VOICES,
- because participants will review the VOICES tool and answer questions on the iPad with the help of the RA, there is a risk of compromised security of personal information,

Many of these adverse events would likely occur as a result of the mandatory report to PSE that the ED would make. However, during this study the ED is expected to discover information that will require the ED to make a report to PSE even if the patient does not want them to do so (and, as noted above, this report may have significant consequences).

11. Minimizing Risks: Describe the manner in which the above-mentioned risks will be minimized.

The Yale ED has a comprehensive, protocolized, and multi-disciplinary process for dealing with EM identification and disclosure and the appropriate next steps and interventions after EM disclosure or identification according to laws, local regulations, and statutory mandates, both on a federal- and state-level. After the start of the study and in the Yale ED, there will be two groups of EM victims: A) those who were identified by VOICES and B) those who were identified by ED providers as part of usual care. The two groups may have similar risks for adverse events, but they are different in one important way. For patients with EM identified by VOICES, the risk is created because of the research intervention and wouldn't occur if VOICES didn't exist or if they declined to participate. Our research team is aware of the potential for the occurrence of adverse events that may be the result of the VOICES screening process. The subsequent ED multi-disciplinary response to EM identification, whether initially identified through VOICES or through ED usual care, is comprehensive and protocolized.

Risks will be minimized through appropriate participant exclusions and close medical supervision throughout the protocol. We will inform all participants that there is a chance that they may experience AE or SAE by participating in the study and that their participation is voluntary. We will also remind participants that they can discontinue participation at any time. In the Yale ED and when a member of the health care team has any suspicion of EM, he or she will notify the ED social worker who has a well-established multi-disciplinary and comprehensive protocol on how to handle the EM cases. The protocol includes any combination of the following: interview, screening (if EM is suspected but not yet identified), referral to community service provider, safety admission to the hospital, or reporting to CT Protective Services for the Elderly (PSE). The hospital, the community, PSE, and the law enforcement agencies have systems in place to maintain the abuse victim's safety.

In Summary: VOICES' goal is to help identify cases of EM within the ED visit. The subsequent procedures for the EM identification are important but are similar to the case when a provider identify suspicion of EM during normal clinical care:

- the ED already (before conducting the VOICES study) has a comprehensive and protocolized multi-disciplinary approach to respond when elder mistreatment is suspected by ED providers during usual clinical care.
- all patients who screen positive with the VOICES tool will receive a similar response.

- while the research team recognizes that the EM identified through the VOICES tool may lead to adverse events for patients associated with EM identification, we anticipate that the Yale ED's response will minimize the possible adverse events due to the EM identification.

We will train all RAs to detect common signs of distress and anxiety. If any are even suspected of being observed, our Co-I ([name]), who is a licensed clinical psychologist, will be contacted immediately for consultation and next steps, which could include counseling, referrals or a psychiatric evaluation

Moreover, a licensed clinical psychologist will be available for consultation to the staff and patient, if needed, during most hours of recruitment. When this level of back-up is not available, we will have psychiatry back-up for any distressed reactions that require mental status evaluation. Thus, some psychological or psychiatric evaluation will be available during all study assessments and during all recruitment periods of the project to facilitate stabilization and necessary referrals for participants who report distress during assessment procedures.

If the older adult screens positive on the VOICES for EM or the older adult wants to self-disclose EM, the RA will notify the care team in the ED that there is suspicion of EM. Also, if the tool fails to identify EM but the patient would like to disclose EM, the RA will notify the care team. The RA will stay with the participant until a member of the care team arrives and implements existing protocols for handling EM in the ED.

The care team can address each patient's concerns around reporting, immediate safety concerns, and any concerns for retaliation or abandonment. The care team will contact the social worker by calling Mobile Heart Beat or his/her cell phone. The social worker will perform the Social Worker Assessment. If the assessment indicates suspicion of abuse, then the social worker will work with members of the multi-disciplinary team to handle the mistreatment case. If the case gets reported to PSE, usually PSE will arrive at the hospital within 12 hours to take care of the case. While waiting for PSE, the health care team members will discuss safety issues with the patient. If the older adult feels s/he is in immediate danger or does not feel safe going home, the care team will create a safe disposition plan that can include safety admission to the hospital until PSE can implement a more permanent solution.

We will protect against psychological distress by informing all participants that there is a chance that they may experience some negative emotions while completing the surveys, after completing survey, or when they leave the hospital, but that they do not have to answer questions that they find distressing. We will also remind participants that they can discontinue participation at any time. We will also provide all older adults that we approach with the brochure on resources for aging well that also include free referral line. These options will be discussed with participants during initial recruitment.

Although privacy and confidentiality will be preserved to the utmost extent possible, participants will be informed that, should EM be identified, the RA will report this to the care team in the ED. For example, if in the course of research procedures, a participant reveals elder abuse to the RA, the RA will discuss with the participant his/her responsibility to report the abuse to the care team in the ED. The care team will do its EM assessment and if they find suspicion of abuse, they will intervene to ensure that ED's EM protocol is implemented. Also, if the participant divulges suicidality, the RA must report this to the care team in the ED and notify the PI.

We will follow standard hospital operating procedures to guard against the possibility of study coercion, loss of confidentiality, psychological distress, and escalation of abuse, acknowledging that awareness or suspicion of reporting may anger the abuser but can also empower the patients and ultimately, make them safer.

Our intent is to conduct a VOICES study session **without the presence** of the caregiver. From our experience, family members usually volunteer to leave the room once the health care provider walks in. When they are asked to leave the room, they usually do so. We will ask the caregivers to leave the room before engaging the older adults in the study and before consenting them. If the older adult wants the caregiver to remain, we will respect their wishes, but that patient will be excluded from the study and no study information will be presented.

Given the sensitive nature of the study topics, along with the safety concerns surrounding elder abuse, RAs will discuss the risk should study materials (e.g., copies of the consent form) be seen by the abuser and will suggest

that such materials be discarded or kept with study staff after review but before leaving the ED. Risks to participants, including pregnant women and their fetuses, are minimal given that this tool will be provided to adults aged 60 years or older. Subjects experiencing adverse events will have access to full in-patient medical facilities of the Yale-New Haven Hospital should intensive treatment be necessary to reverse any complications during the study.

If a participant reveals depression, the research assistant will provide a referral to a mental health agency accessible to the subject. If a participant reveals severe depression or suicidality, or requests immediate psychiatric care for any reason, the RA will alert the patient's clinician to initiate an immediate psychiatric evaluation.

The RAs will receive training for all procedures related to suicidality and elder abuse.

Since the VOICES tool is a web-based application in nature, **no information** will be stored on the tablet. If the tablet gets lost or stolen, the patient's data will not be compromised. All iPads contain encryption software, per University Policy 5100.

12. Data and Safety Monitoring Plan: Include an appropriate Data and Safety Monitoring Plan (DSMP) based on the investigator's risk assessment stated below. (Note: the HIC will make the final determination of the risk to subjects.)

The DSMP will be monitored by the study team. The Principal Investigator (PI) will be responsible for ensuring participants' safety on a daily basis. To ensure that we are identifying both the adverse events that we might anticipate as well as those that you might not, the PI will review each case where either: (1) a report was made to PSE or (2) a patient was admitted to the hospital for safety to assess for any potential adverse events. The Data and Safety Monitoring Team (DSMT) will consist of Drs. [name], [name], [name], [name], and [name]; this team will monitor participant safety, evaluate the progress of the study, and review procedures for maintaining the confidentiality of data, the quality of data collection, management, and analyses. They will monitor the study for reports of any adverse or unexpected events. Study participants will be advised to contact the study team to report any adverse events or concerns. VOICES will only be administrated for the intervention group, and there will be no control groups. The PI and investigative team will monitor data and safety at the monthly study team meetings. The following will be reviewed:

- Cumulative accrual
- Enrollment of subjects who meet the study eligibility criteria only
- Recruitment is proceeding as planned
- The informed consent process is conducted appropriately; informed consent is obtained
- Evaluate the progress of the trial, including periodic assessments of data quality and timeliness, recruitment, accrual and retention, participant risk versus benefit, and other factors that can affect study outcome
- Consider factors external to the study when relevant information becomes available, such as scientific or therapeutic developments that may have an impact on the safety of the participants or the ethics of the trial
- Review study performance, make recommendations, and assist in the resolution of problems reported by the PI
- Evaluate data completeness and quality and as specified in the protocol.

Prior to proceeding with any study procedures

- Review the research protocol, informed consent documents and plans for data safety and monitoring
- Protect the safety of the study participants
- Ensure the confidentiality of the study data and the results of monitoring
- Review procedures for the privacy and confidentiality of subjects
- Review cumulative attrition and attrition by gender and race/ethnicity
- Review dropouts and reason for withdrawal from the study are documented

The principal investigator will be responsible for monitoring the data, assuring protocol compliance, and conducting the safety reviews. During the review process the principal investigator will evaluate whether the study should continue unchanged, require modification/amendment, or close enrollment.

The principal investigator and the Institutional Review Board (IRB) and the NIA have the authority to stop or suspend the study or require modifications.

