In this exploratory aim, we will evaluate the *positive predictive value* of VOICES as a screening tool in correctly identifying EM cases. This could serve as preliminary test for the accuracy of VOICES in correctly classifying victims/non-victims. It will be estimated through the measure of positive predictive value (PPV) using the APS case outcomes as the gold standard comparison.

Design and rational:

In Connecticut, reported cases of EM are investigated by the Protective Services for the Elderly (PSE), commonly known as APS, which is administered by the Division of Social Work Services within the Connecticut Department of Social Services (please see letter of support). PSE is designed to safeguard people age 60 and older from EM. Pursuant to State Code 2012-R-0437, mandatory reporters are able to know outcomes of their report (see letter of support from PSE). If a case was opened by PSE this means the case met the state's determined threshold for a situation requiring an investigation so reporting was valid. Often times, if a case was opened regardless of EM determination services are provided to the older adult. For our purposes, PPV is a measure of VOICES ability to correctly classify cases of clinically significant EM (true positive rate). Determination by PSE will serve as our gold-standard criterion for comparison. Ideally, VOICES would only refer cases which would require an investigation and have a positive finding of EM as this would represent true validity in identifying positive cases.

VOICES-C Study: (01/10/2020 to 03/01/2020) completed

We will conduct this activity to formally evaluate the usability of the VOICES tool. Usability refers to how easily a specific task can be accomplished with a specific tool. The International Organization for Standardization (ISO) defined usability as the "extent to which a product can be used by specified users to achieve specified goals with effectiveness, efficiency and satisfaction in a specified context of use" (ISO, 1998). Hypothesis 1a: users will report a high level of ease of use of VOICES. Hypothesis 1b: Users will report a high level of satisfaction in using VOICES.

What will subjects be asked to do?

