4. OUTCOMES

The primary and Other Pre-Specified Outcome Measures are summarized in Table 1.

Table 1. Primary and Other Pre-Specified Outcome Measures		
Domain	Measure (P,O)	Source and Frequency
Implementation	Participation. Participation will be determined by the ratio of participants who are successfully enrolled to the total	Study enrollment records

	number of eligible patients. (P)	
	Usage. Usage will be determined by the number of consented participants enrolled in the study who used VOICES to completion (P)	VOICES tool completion records
Acceptability	Participant satisfaction measured using post-use satisfaction survey with two 5-point Likert response set scales, developed by the research team (O)	Self-report, once per participant
Demand	Measured by the % of the patients who self-identified with elder mistreatment and the % who receive the Brief Negotiation Interview (BNI) portion of VOICES.	Measured by VOICES tool, once per participant
	Average time to consent & orient participants to the tool (O)	RA measurement, once per participant
Practicality	Average time needed to complete VOICES (O)	RA measurement, once per participant
	Average time patients perceived time of VOICES	Self-report, once per participant
Efficacy of the Educational Material	Measured as % of participants that change their self-identification response after completing the educational component (O)	Measured by VOICES tool, once per participant
Efficacy of the Brief Negotiation Interview	Measured as % participants that change their self-identification response after completing the educational component (O)	Measured by VOICES tool, once per participant
Efficacy of Self-Identification on Self-Disclosure	Measured as % of patients who disclose among those who self-identified (O)	Measured by VOICES tool, once per participant
Accuracy	Measured as percent of classified EM cases that were positive based on social worker assessment, and those referred to Adult Protective Services (APS). (O)	Measured by the outcome of the social worker assessment and by the outcome APS evaluation.
EM: Elder Mistreatment; BNI: Brief Negotiation Interview; APS: Adult Protective Services		

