7.2 Analysis of Other Pre-Specified Outcomes

Acceptability: Participant satisfaction will be measured along multiple dimensions using post-use satisfaction survey with two 5-point Likert response set scales, developed by the research team. Scale 1: Likert scale 1-5, where 1= Very Dissatisfied, and 5= Very Satisfied Scale 2: Likert scale 1-5, where 1= Strongly Disagree, and 5= Strongly Agree. The means and standard deviations will be reported.

Demand: Demand will be assessed through examining how likely will VOICES be used by patients. To do this, the size of target population of EM victims in the ED will be measured by the % of the patients who self-identified with elder mistreatment and the % who receive the Brief Negotiation Interview (BNI) portion of VOICES. Counts of participants will be reported.

Practicality: Practicality will be assessed by observing the ease of VOICES use by patients. To do this, a series of steps will be watched to determine the efficiency of implementation measured by the average time (1) to consent & orient participants to the tool and (2) needed to complete VOICES documented by the Research Assistant; and (3) patients perceived time of VOICES as measured on post-survey. Each of these will be reported as part of the overall outcome. The means and standard deviations will be reported.

Efficacy of the Educational Material: To understand the efficacy of VOICES in this pilot, we will look at how many participants changed their self-identification response after completing the educational component. Counts of participants will be reported.

Efficacy of the Brief Negotiation Interview: We will look at how many patients changed their readiness to identify and readiness to disclose after completing the Brief Negotiation Interview (BNI). Counts of participants will be reported.

Efficacy of Self-Identification on Self-Disclosure: We will explore whether self-identification impacts likelihood of self-disclosure. Counts of participants who change willingness to disclose among those that self-identify will be reported.

Accuracy: To understand the accuracy of the VOICES tool, a preliminary evaluation of the accuracy of VOICES as a screening tool in correctly classifying EM cases that were positive based on social worker assessment, and those referred to Adult Protective Services (APS). The percent correct classification will be reported.

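### The SAP has no place for participants whom VOICES misses but who disclose to the research assistant, so a sensitivity computed from its classified cases would be 100% by construction

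*Protocol*

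**What the plan says.** Protocol item 11 (Minimizing Risks) has the research assistant (RA) alert the care team when a participant screens positive or wants to self-disclose. It then adds: "if the tool fails to identify EM but the patient would like to disclose EM, the RA will notify the care team". The same item covers a second route, "if in the course of research procedures, a participant reveals elder abuse to the RA", after which the RA must report it and the care team makes its own assessment. The care team contacts the social worker, and "The social worker will perform the Social Worker Assessment".

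Accuracy is described in four ways:

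- Protocol, Specific Aim 3: "It will be estimated through the measure of positive predictive value (PPV) using the APS case outcomes as the gold standard comparison".
- SAP section 4, Table 1, Accuracy row: "Measured as percent of classified EM cases that were positive based on social worker assessment", with referral to Adult Protective Services (APS) as a further reference.
- SAP 4.2 and 7.2: an evaluation of how well VOICES classifies cases that the social worker found positive, ending with "The percent correct classification will be reported". Neither section states a denominator.
- SAP 6.1: a finding of sensitivity with 95% confidence intervals, beside an expected 40 to 70 detections.

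For disclosure, the SAP (Table 1 and 7.2) restricts the measure to participants who self-identified, and Table 1 names the VOICES tool as its source. Protocol Table 1 gives the change in the percentage who disclose without that restriction.

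Neither document has an outcome, table row or rule for a participant whom the tool does not identify and who tells the RA.

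**The concern.** A tool-negative participant who discloses to the RA and is confirmed by the social worker is a false negative that the study has seen. Apart from cases found by usual care, these are the only tool-negative participants for whom the documents describe a route to a reference assessment. They are therefore the only direct evidence the study can have of what VOICES misses.

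An analyst who follows Table 1 would start from classified cases and never meet them. For a PPV that is correct. It is not correct for sensitivity, which is defined by misses, and it leaves percent correct classification open to more than one meaning. The final report could show a favourable sensitivity or percent correct while RA observations or case reviews from the same study held known misses.

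**Working it through.** **Inputs from the documents.** Protocol item 13 gives N = 800 and an expected elder mistreatment prevalence of 5.7% to 9.12%, hence 45-72 adults. SAP 6.1 expects 40 to 70 detections. The SAP reports 1002 recruited.

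**The plan's own figure.** 800 × 0.057 = 45.6 and 800 × 0.0912 = 72.96; rounded down, these give 45-72. The SAP's 40 to 70 is similar but has no arithmetic behind it. No stated figure is wrong on account of this point.

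**Definitions.** Let TP and FP be classified cases that the reference confirms or does not confirm. Let m be confirmed misses that the study observes, and u be misses among tool-negative participants who stay silent and get no reference assessment.

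- PPV = TP/(TP + FP). Neither m nor u appears in it.
- Sensitivity in the sample = TP/(TP + m + u).
- From classified cases alone, m and u are both absent, so the result is TP/TP = 1.
- With observed misses, apparent sensitivity = TP/(TP + m). Since u is at least 0, this is an upper bound.

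**Illustration.** The documents give neither a PPV nor m, so both are assumed. With PPV 0.8, 40 classified gives TP = 32 and 70 classified gives TP = 56. Intervals are Clopper-Pearson 95%.

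| m | PPV | Apparent sensitivity, 40 classified | Apparent sensitivity, 70 classified |
|---|---|---|---|
| 0 | 0.80 | 1.000 (0.891-1.000) | 1.000 (0.936-1.000) |
| 1 | 0.80 | 32/33 = 0.970 (0.842-0.999) | 56/57 = 0.982 (0.906-1.000) |
| 5 | 0.80 | 32/37 = 0.865 (0.712-0.955) | 56/61 = 0.918 (0.819-0.973) |
| 10 | 0.80 | 32/42 = 0.762 (0.605-0.879) | 56/66 = 0.848 (0.739-0.925) |

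With PPV between 0.5 and 1.0 and m = 10, apparent sensitivity runs from 20/30 = 0.667 to 70/80 = 0.875.

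**What percent correct could mean.** Take 40 classified, TP = 32 and m = 5.

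- As a PPV: 32/40 = 80%.
- As overall accuracy among 1002, with every other tool-negative participant assumed to be a true negative: 1002 − 40 − 5 = 957 true negatives, and (32 + 957)/1002 = 989/1002 = 98.7%.

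The SAP does not say which of these it would report.

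**The case against.** The strongest reply is that a PPV should exclude false negatives. The protocol names a PPV, and SAP Table 1 describes one. A reader might infer that the planned Accuracy figure is too high because it leaves misses out. The documents do not support that: the PPV does not depend on m, and it should stay as defined.

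A reader might also infer that the plan settles the matter and throws known cases away. It does not say so. SAP 4.2 and 7.2 can be read as covering every social-worker-positive case, including those the tool missed, and the sensitivity in SAP 6.1 would need them. Protocol item 4 lists RA observations on each participant as a data source, and under item 12 the principal investigator reviews every case with a report to the state's Protective Services for the Elderly (PSE) or a safety admission. What stands is that the only stated denominator in the SAP excludes these participants and no rule brings them in.

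It is tempting to extend the criticism to the disclosure outcome, but that goes too far. Its denominator is self-identification, which is not the same as a positive screen. One of the protocol's two descriptions of the session puts the self-identification question without limiting it to screen-positives, so a screen-negative participant could self-identify in the tool and be counted. Restricting to self-identifiers also follows from the question that outcome asks. What remains is narrower: someone who answers no in the tool and then tells the RA has no line in the SAP.

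Three cautions also stand. Volunteered misses depend on willingness to speak to the RA. Adding them to the classified-case percentage would give 32/45 = 71% in the example above, which is neither PPV, sensitivity nor accuracy. A disclosure is not a confirmed miss until it is assessed, and PSE is involved only if the case is reported.

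**Conclusion.** The point holds as a gap in definition and reporting. The protocol foresees tool-negative disclosers who can obtain a reference result. The SAP's one Accuracy measure with a stated denominator omits them, yet the SAP also promises a sensitivity and a percent correct classification. A sensitivity taken from classified cases alone would be 100% whatever the tool's performance.

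The size is unknown. The documents give no expected number of such cases, and it may be zero. At an assumed PPV of 0.8, 5 to 10 confirmed misses would put apparent sensitivity between 0.762 and 0.918 in place of 1.00; this shows the direction and is not a forecast. The conclusion rests on reading Table 1 as the operative definition. If the sponsor intends 4.2 and 7.2 to include misses, the same clarification is needed. If sensitivity in SAP 6.1 was meant loosely, the word should go.

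The point is minor: Accuracy is an exploratory, preliminary evaluation and not a primary outcome.

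**What to change.** In SAP 4.2, 6.1 and 7.2:

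1. Call the Table 1 measure a PPV and give its denominator, in place of percent correct classification.
2. Beside it, report the number of VOICES-negative participants who disclosed mistreatment to the RA, zero included, with their social worker result and, where reported, the PSE result. Label it the minimum number missed. State whether VOICES-negative refers to the screen or to the self-identification answer.
3. Count the confirmed ones as false negatives in any sensitivity that is reported and label that figure an upper bound, or drop the term. Do not add them to the PPV denominator.
4. List disclosures made to the RA on a separate line from disclosures made in VOICES.

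Because the SAP states that 1002 participants have been recruited, the count has to come from existing RA observations and case review records. If it cannot be recovered, the report should say so.

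The cost is a few lines of SAP text, some extra table rows and a search of existing records. No new assessment is needed, since these participants already enter the care pathway. The downside is that accuracy may look slightly less favourable.

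### The PI's adverse-event case review is triggered only by a PSE report or a safety admission, so flagged participants discharged without either, and distress escalations, fall outside it

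*Protocol*

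**What the plan says.** Protocol section 12 (Data and Safety Monitoring Plan) states a broad purpose for the PI's case review: "To ensure that we are identifying both the adverse events that we might anticipate as well as those that you might not". Its scope is then two outcomes, since the PI's task is to "review each case where either: (1) a report was made to PSE or (2) a patient was admitted to the hospital for safety". PSE is Connecticut's Protective Services for the Elderly.

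Section 11 (Minimizing Risks) describes what happens to a participant flagged for elder mistreatment (EM):

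- Flagging is wide: either a positive screen or a wish to disclose is enough for the research assistant to inform the care team.
- The next step depends on the social worker: "If the assessment indicates suspicion of abuse, then the social worker will work with members of the multi-disciplinary team to handle the mistreatment case".
- The ED response has several possible parts, of which safety admission and a PSE report are only two: "The protocol includes any combination of the following: interview, screening (if EM is suspected but not yet identified), referral to community service provider".

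Section 10 (Risks) lists psychological harm in its own right: "distress/anxiety during and/or after using the VOICES tool is a potential risk". Section 11 provides for it: "We will train all RAs to detect common signs of distress and anxiety". Suspected distress goes at once to a co-investigator who is a clinical psychologist, with psychiatry as back-up. Section 12.1 defines an adverse event (AE) as an undesirable, unintended effect that follows directly from use of the tool.

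**The concern.** The review's purpose covers all adverse events, but its triggers cover two dispositions. Two groups fall between them.

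The first is flagged participants who go home with no PSE report and no safety admission. Section 11 says, of patients identified by VOICES, that the research itself creates the risk. It also recognises that an abuser may be angered by the mere suspicion of a report. Neither statement requires that a report was made.

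The second is participants distressed by the tool. Among the harms in section 10, distress fits the AE definition in section 12.1 most directly. Yet a call to the psychologist or to psychiatry does not trigger the review, and no section says that it is recorded as an AE.

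At stake is how complete safety ascertainment is in a single-arm study, where case-by-case review is a main means of recognising harm from the intervention.

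**Working it through.** This is a question of scope, so the main check is to trace each kind of participant through the Protocol.

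| Participant | Meets a section 12 trigger? | Other documented route to the study team |
|---|---|---|
| Flagged, reported to PSE or admitted for safety | Yes | PI case review |
| Flagged, social worker finds no suspicion, goes home | No | Post-survey in the ED; self-report afterwards |
| Flagged, interview or community referral only | No | Post-survey in the ED; self-report afterwards |
| Distress seen or suspected by the research assistant (RA) | No | Psychologist co-investigator or psychiatry back-up; AE recording not stated |
| Suicidality disclosed | No | Care team, and the PI is notified (section 11) |
| Stopped because of distress | No | Reason for non-completion on the post-survey (Protocol Table 1); withdrawals reviewed (section 12) |

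The post-survey also asks about safety concerns (Table 1). It is completed at the end of the ED session (section 4), so it cannot capture what happens at home. No scheduled contact after the visit is described. The remaining route after discharge is the advice in section 12 to contact the study team. Section 11 has RAs suggest that study materials be discarded or left with staff in case an abuser sees them, which shows why self-report may be weak in this population.

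**Scale.** Protocol section 13 expects 45 to 72 EM cases among 800. This reproduces: 800 × 0.057 = 45.6 and 800 × 0.0912 = 72.96, both truncated. SAP section 6.1 expects VOICES to detect 40 to 70.

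**Review load if every flagged case is reviewed.** Over the SAP's 16 months, 40 / 16 = 2.5 and 70 / 16 = 4.4 a month, or about 3 to 5 when rounded up. Over the 21 months of recruitment in Protocol section 6, the Protocol's counts give 45 / 21 = 2.1 and 72 / 21 = 3.4. Both treat expected EM cases as if they were flagged participants. False-positive screens and distress calls would add to them.

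**Number outside the current review.** This is F × (1 − r), with F the number flagged and r the share reported to PSE or admitted for safety. The documents give no r. As an assumption only, r from 30% to 80% with F from 40 to 70 gives 40 × 0.2 = 8 up to 70 × 0.7 = 49. With r near 1 the number is near zero. The range shows how far the answer depends on r; it is not an estimate.

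**The case against.** The best defence has four parts.

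- **Other routes exist.** RAs watch for distress and escalate on suspicion, suicidality goes to the PI, the post-survey asks about safety, withdrawals are reviewed, and the Data and Safety Monitoring Team (DSMT) monitors any reported event. This stands. A reader might infer that the uncovered participants are never reviewed, or that the case review is the plan's only active search for harm; the documents contradict both. The answer is narrower: these routes mostly act on what has been noticed or reported, and no text links a distress call to AE assessment.
- **The triggers have a rationale.** Section 10 attributes many of the listed harms to the mandatory PSE report. That explains why reported cases come first. It does not cover distress from using the tool, and many is not all, while the stated purpose includes unexpected events.
- **No planned estimate is affected.** A reader might infer that a reported adverse-event rate would be too low. The SAP lists no such rate among its outcomes, so the effect is on monitoring and on any AE summary, not on a planned endpoint.
- **Wider review would not find retaliation at home.** This also stands. Reviewing more cases adds no information from after discharge.

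**Conclusion.** The point holds in limited form. The PI case review is narrower than its stated purpose. Flagged participants discharged with neither trigger lie outside it and depend on self-report afterwards, and distress escalations are linked neither to the review nor to AE recording. This follows from the text of sections 10 to 12 and needs no assumption.

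The size cannot be derived. It is tempting to put a count on the cases missed, but any such count rests on an assumed reporting share. Mandatory reporting in Connecticut could make that share high. The SAP's 40 to 70 is also a forecast of EM detected, not a count of care-team notifications. The plan should be changed because the gap is specific and cheap to close, not because a known number of harms is being lost.

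**What to change.** Widen the section 12 trigger so that the PI also reviews:

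1. every participant for whom the care team was notified of suspected EM, whatever the PSE or admission outcome; and
2. every participant for whom psychological or psychiatric back-up was called, or who stopped VOICES because of distress.

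State that each such case is assessed for AE status, and report the cases with their disposition to the monthly meeting and the DSMT.

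The SAP's Study Summary and section 3 describe 1,002 participants as already recruited. If recruitment is complete, apply the same criteria retrospectively from existing records, and state when reporting AEs that ascertainment during the study was narrower.

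The cost is a short amendment and the monthly review load worked out above, with no new staff or visits. The RA makes the notifications and works to the distress pathway, so the cases should be identifiable where records were kept. The change concerns monitoring only and leaves care as it is.
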